Aim 2 (Efficacy): Evaluate whether the self-guided repetitive artmaking kits significantly impact patients' self-reported experiences of pain, mood (inclusive of depression and anxiety), and social isolation. *Hypothesis 2: Repetitive artmaking will reduce experiences of pain for patients with both chronic pain and OUD/opioid misuse.* Acceptance criteria: Significant pain reduction during artmaking practice as captured using the first three questions of the BPI Reduced Minus Peg Questions 8-item questionnaire (attached) – questions one and two will be only asked in the pre-survey as these questions ask about pain over the last week and will therefore not change before and after a solo artmaking experience. We also propose to have patients complete the 6-item Pain Catastrophizing Questionnaire (attached) during the in-person workshop to gain an understanding about patients' experiences of pain. This data will be supplemented with qualitative data from the meaning making session and storytelling content, for those who participate. *Hypothesis 3: Repetitive artmaking will reduce depression and anxiety and improve mood for patients with chronic pain and OUD/opioid misuse.* Significance improvements in mood (anxiety and depression) during artmaking practice as captured using single survey questions asking patients to rate their current experiences of anxiety and depression. This data will be supplemented with qualitative data from the meaning making session and storytelling content, for those who participate. *Hypothesis 4: Supporting patients with chronic pain and OUD/opioid misuse in making art will result in higher ratings of social connectivity.* Significant improvement in social connectivity during artmaking practice as captured using the IOS-CC (attached). *Hypothesis 5: Repetitive artmaking will reduce opioid misuse in patients.* Any reduction in non-prescribed opioid use as captured by a question asking patients if they have used non-prescribed opioids in the past 24 hours (modified from the Addiction Severity Index question about recent opioid use) as both a measure of opioid use in connection with artmaking and we will be evaluating patients' opioid use over the course of the study, and a question asking patients to share how high they are at the time of the survey (from the Modified DFAQ-CU Inventory but focusing on opioids not cannabis). This

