In-Person Workshop: [name], an Art Therapist, will lead three (3) two-hour in-person workshops at [name], with all patients required to attend one (1) in-person workshop as part of this study. Spanish translation will be available at all workshops. The purpose of these workshops are twofold: they will gather patient characteristic data (demographics, Pain Catastrophizing Survey, questions on experience with art and openness to mindfulness) and orient patients to the use of the art kits available to them to take and use at home. The art therapist will develop three (3) repetitive artmaking kit options and will develop enough for patients to leave the workshop with one of each kit. Preliminary options include mandala painting and macramé, with the final kits to be developed during the planning phase in partnership with the IMPOWR-ME Community Leadership Board. As previously stated, the art kits will be compiled to minimize visual identification from others that they are part of a research study, with all survey materials asking sensitive questions buried in the middle of the packet. At the start of the in-person workshop, the PI will orient patients to the pilot goals and activities, answer all questions, collect consent forms, and provide the link to the pre-survey assessing pain and mood as well as paper versions of the survey. [name] will provide an engaging overview of the three available kits, and patients will select a kit to try for the in-person workshop. [name] and the Study Coordinator will be present to provide Spanish translation and explanation as necessary. The last 15 minutes of the workshop will be saved for patients to complete the post-survey on pain and

mood and to remind patients that they will be compensated for using the art kits at home up to four (4) times if they complete pre- and post-surveys. Finally, patients will be informed that they will be invited to bring their artistic outputs to be photographed by a professional photographer ([name]) at the end of the four-month period and to share their experiences of making the art, so that they can share what they have made with the broader community. It will be made it clear that displaying their art and sharing their experiences is not mandatory, that patients do not need to decide during the workshop if they will want to share their artwork, and that they will be able to use full, part, or none of their name in the event.

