At-Home Artmaking: Patients will be invited to take home all three (3) art kits at the end of the in-person workshop, each of which will allow them to make multiple versions of the type of art in question (aka materials for multiple mandalas). Each kit will include multiple copies of the pre- and post-survey assessing pain and mood and a reminder to complete the pre- and post-survey when doing the kits to receive an incentive of \$20 compensation for up to four (4) times within a four-month period (the end date will be included in the art kits). Communication from the Survey Coordinator will also include the links to the pre- and post-surveys. The instructions will prompt patients to complete the survey immediately before starting the art kit and immediately after concluding. Patients will further be prompted to include a photo of their art in the post-survey if they are using the online survey system, or they can text their photo to the Study Coordinator if they have phone-based photography capacity. All instructions will be in English and Spanish. This implementation process is designed to assess real-world use of the art kits.

Data Collection:

Event	Data Collection Method	Measures to be Collected
In-Person Workshop	Patients complete online pre- and post-survey via a QR code or paper form	
 • Questions 1-3 of the BPI Reduced Minus Peg Questions (pre) and question 3 of the BPI Reduced Minus Peg Questions (post) • Pain Catastrophizing Questionnaire • Single question asking about current level of depression • Single question asking about current level of anxiety • IOS-CC • Questions asking about current and recent unprescribed opioid use (pre) and level of highness in the moment (pre, post) • Single question asking about experience with art • Single question asking about openness to mindfulness activities
At-Home Artistic Practice #1	Patients complete paper pre- and post-survey	
 • Questions 1-3 of the BPI Reduced Minus Peg Questions (pre) and

At-Home Artistic Practice #2		question 3 of the BPI Reduced Minus Peg Questions (post) 
 • Single question asking about current level of depression • Single question asking about current level of anxiety • IOS-CC • Questions asking about current and recent unprescribed opioid use (pre) and level of highness in the moment (pre, post)
At-Home Artistic Practice #3		
At-Home Artistic Practice #4		

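### The workshop pre-survey is given out before the kit overview and kit choice, with no set completion time, so on the natural reading the workshop change covers more than artmaking, unlike the home pairs

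*Combined protocol and SAP*

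**What the plan says.** All references are to the combined protocol and SAP.

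- **Target of the hypotheses.** Section 1, Aim 2, sets the criterion for Hypothesis 2 as "Significant pain reduction during artmaking practice". Hypotheses 3 and 4 are framed the same way for anxiety, depression and social connectivity.
- **Workshop order.** Section 3, In-Person Workshop, describes a session of two hours. It opens thus: "At the start of the in-person workshop, the PI will orient patients to the pilot goals and activities, answer all questions". In the same step the PI is to "collect consent forms, and provide the link to the pre-survey assessing pain and mood as well as paper versions of the survey". Next, a member of the team (name removed; presumably the art therapist, who leads the sessions) "will provide an engaging overview of the three available kits, and patients will select a kit to try for the in-person workshop". At the end: "The last 15 minutes of the workshop will be saved for patients to complete the post-survey on pain and" mood, with a reminder about payment for home use in the same slot.
- **Home order.** Section 3, At-Home Artmaking: "The instructions will prompt patients to complete the survey immediately before starting the art kit and immediately after concluding".
- **Analysis.** Section 3, Data Analysis, plans paired t-tests on the pre/post changes, and linear regressions with baseline controls. It does not say whether workshop and home pairs are analysed together or apart.

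**The concern.** With no comparison group, the placing of the two surveys is the main thing that ties an observed change to artmaking. Whatever happens between them enters the paired difference. At home the protocol places both surveys at the edges of the activity. At the workshop it does not: the form is handed out before a guided group introduction and a choice among three kits, neither of which is the self-guided practice under test.

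Ratings of current anxiety, depression and social connection could respond to such an introduction before any art is made, and the difference would then be read as an effect of artmaking. Attendance at one workshop is required of every patient, while home pairs are optional, up to four each, and Section 4 expects high attrition. The workshop pair may therefore carry real weight in the results.

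**Working it through.** The plan states no figure that bears on this point, so the check is a comparison of the texts plus one bound.

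**Step 1: what lies between the two surveys.**

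| | Workshop | Home |
|---|---|---|
| Pre-survey | Provided in the opening step, after orientation, questions and consent forms; no completion time stated | Directly before the kit is begun |
| Between the surveys | Kit overview, kit selection, artmaking | Artmaking |
| Post-survey | In the last 15 minutes, a slot shared with the payment reminder | Directly after finishing |

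If the form is completed when it is handed out, the workshop window contains two steps that the home window does not. No instruction like the home one is given for the workshop.

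**Step 2: bound on the workshop window.** The session lasts 2 × 60 = 120 minutes, and the post-survey slot takes the last 15. At most 120 − 15 = 105 minutes therefore precede that slot. Orientation, questions and consent come before the hand-out. If they take c minutes, the window from hand-out to the opening of the slot is 105 − c.

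**Step 3: share that is not artmaking.** If the overview and kit selection take s minutes, their share of that window is s / (105 − c). The protocol gives neither s nor c, so the share cannot be computed.

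**Step 4: whether analysis could repair it.** Analysing the two settings separately, or adding a setting term, would show whether workshop and home changes differ. It could not divide the workshop change into a part due to the overview and a part due to artmaking, because nothing is measured between them.

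**Step 5: the closing end.** The last slot holds both the survey and the payment reminder. The text does not require the survey to come first, or to be completed as soon as a patient stops.

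**The case against.** **Hand-out is not completion.** The protocol says when the form is provided, not when it is filled in, and the workshop text is a narrative rather than a timed agenda. This stands as a limit. Early completion is the natural reading; if it is not what is meant, a sentence fixing the time is still needed.

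**The workshop may not be the main evidence.** Its stated purposes are to collect patient characteristics and to introduce the kits, and the Overview ties the home sessions to real-world efficacy. No text says that workshop pairs are pooled with home pairs or decide Hypotheses 2 to 4. This also stands. But workshop pairs are collected and not excluded from the analysis, and the workshop window is wider than artmaking whether or not they are pooled.

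**Reordering does not make the settings equal.** The workshop would still be a group session led by a therapist. That is correct, and it is why separate reporting belongs in the fix.

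**A baseline taken after an engaging overview may be coloured by expectation.** This is speculative, and it applies equally to the home sessions, which also follow the overview.

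Three stronger readings are tempting, and the documents do not support them:

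- A reader might infer that the baseline is taken on arrival, among strangers. Orientation, questions and consent come first, and all patients are recruited from one clinic.
- A reader might put a number on the share. Assuming 20 to 40 minutes for overview and selection gives 20/105 = 19% to 40/105 = 38%. The numerator is a guess, and the denominator starts at the opening of the session rather than at the hand-out.
- A reader might conclude that the workshop result is biased in favour of the kits. That direction is plausible for anxiety, mood and the IOS-CC, but nothing in the documents shows it, and the case is weakest for pain.

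**Conclusion.** The point holds as a mismatch between the workshop procedure and the protocol's own target and home rule. If the pre-survey is completed when provided, the workshop change measures overview, kit choice and artmaking together, and the parts cannot be separated afterwards. The size is unknown: the window before the post-survey slot is at most 105 minutes, less an unstated time for orientation and consent, and the part that is not artmaking has no stated length. No figure in the plan changes. In an exploratory pilot of about 40 patients this affects interpretation and the comparability of the two settings; it does not invalidate the design. It is a cheap improvement, but it has to be made before the workshops run, because the missing measurement cannot be recovered later.

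**What to change.** 1. Have patients complete the repeated workshop pre-survey items (pain, depression, anxiety, IOS-CC, opioid-use questions) after they have chosen a kit and directly before they start it.
2. Have them complete the post-survey as soon as they stop, ahead of the payment reminder and the information about photography.
3. Leave consent and the one-off characteristics (demographics, Pain Catastrophizing Questionnaire, art experience, openness to mindfulness) at the start of the session.
4. State in Data Analysis that workshop and home pairs are reported separately, since the workshop remains a therapist-led group session whatever the survey timing.

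**Cost.** The agenda is reordered and a sentence is added to the analysis text; no new data or staff are needed. The workshop survey set, listed together in the Data Collection table, is split into two administrations, which takes a little handling. The observed workshop change may also be smaller.

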3. RESEARCH DESIGN AND METHODS

Overview:

The proposed pilot is an exploratory evaluation of whether repetitive artmaking in home environments is acceptable for chronic pain self-management in individuals with OUD/opioid misuse, and whether self-driven repetitive artmaking can offer respite from pain, depression, and anxiety, and improve social connectivity. The study will recruit approximately 40 individuals living with chronic pain with an OUD diagnosis or opioid misuse from a Montefiore-led methadone clinic, [name]. The Principal Investigators (PIs) will collaborate with an Art Therapist to develop three (3) simple art kits. Patients will participate in an in-person art workshop, to be held in English with the support of a Spanish translator, and complete pre- and post-surveys assessing in-the-moment pain, anxiety, depression, and social connectivity. Patients will be given all three (3) kits to take home and offered financial incentives to complete the same pre- and post-surveys and art kits at home up to four (4) times within a four-month period to assess real-world adoptability and efficacy. The art kits will not include any visible information about Montefiore or the study in the front of the packets; paper versions of the survey will be enclosed within the kits, to support confidentiality. All patients will be invited to a virtual meaning making group to capture qualitative feedback. The study staff will not share the names of patients with anyone outside the core research team – the co-PIs, Study Coordinator, Patient Advocate, Biostatistician, Art Therapist, and Photographer and Exhibit Coordinator. All patients will be invited to have their art photographed and share their experience of the artmaking process and how it relates to their chronic pain and opioid use. Photographs and stories will be shared on the Montefiore campus as an art exhibit, and the layperson audience will be surveyed to assess any resultant alteration in feelings of stigma toward the population of those living with chronic pain and OUD/opioid misuse. Patients who share their artwork will be able to decide if they want their name (or a portion of their name) or a pseudonym to be included in the exhibit alongside their artwork, or if they would like to maintain anonymity.

Implementation:

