6. INFORMED CONSENT

Informed consent will be conducted by the Study Coordinator as follows: all potential patients will complete a brief oral consent and then complete the eligibility screener. This process can take place in-person in a private room at [name] or over the phone in the case of patients who wish to be screened at a time of their choosing as opposed to when they encounter the study team. If eligible, the Study Coordinator will explain the study and any risks and benefits, and obtain written informed consent.

Remuneration:

Patients will receive \$50 for participating in the in-person workshop and will be incentivized to use the art kits at home and complete pre- and post-testing for up to four times with \$20 each time. Further, all patients will be invited to participate in a meaning making session to capture qualitative feedback on the feasibility of the project; if they attend, they will be compensated \$50 for their participation. Patients will be compensated through a Clincard in their name. These cards include no information that link them to the study or indicate that this compensation is related to a study.

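### The four paid home survey pairs need no gap between them, so the 24-hour opioid item (Hypothesis 5) can count the same hours several times

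*Combined protocol and SAP*

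**What the plan says.** Section 3 (Overview) has patients repeat the surveys and kits "at home up to four (4) times within a four-month period to assess real-world adoptability and efficacy". The At-Home Artmaking paragraph repeats the cap, "up to four (4) times within a four-month period", and adds only an end date. Section 6 (Remuneration) offers payment to "complete pre- and post-testing for up to four times with" $20 each time and attaches no timing condition.

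All three kits leave the workshop with the patient, "each of which will allow them to make multiple versions of the type of art in question", and each kit holds several copies of both surveys. The only timing instruction is to fill in the surveys directly before and directly after a session. The monthly check-ins ask about kit use and barriers; they do not schedule sessions.

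For Hypothesis 5, Section 1 asks patients "if they have used non-prescribed opioids in the past 24 hours". It gives this item two purposes: use in connection with artmaking, and "opioid use over the course of the study". The data collection table places the opioid-use questions in the workshop pre-survey and in every home pre-survey. BPI questions 1 and 2 are also in each pre-survey, and "these questions ask about pain over the last week".

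Data Analysis names paired t-tests and linear regressions with baseline controls. It does not mention session order or the interval between sessions.

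**The concern.** A repeated item with a 24-hour look-back gives separate observations only if the surveys are at least 24 hours apart. The plan does not require that, and it pays per completed pair, so same-day sessions are compliant and paid.

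For Hypothesis 5, bunched surveys report largely the same hours. A single episode of use can then be counted several times, and the repeated reports say little about use across four months. The success criterion is any reduction, so even a small artefact matters. An episode 23 hours before the first of two starts gives a yes; two hours later the same episode is 25 hours old and the answer becomes no. That looks like a reduction but rests on two new hours of observation.

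For Hypotheses 2 to 4 the issue is weaker. If a session improves pain, mood or connectedness and the effect lasts until the next start, the next pre score is already improved and the measured change is smaller.

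**Working it through.** The plan gives no figure on this point, so there is nothing to reproduce.

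**Inputs from the documents:** four paid home sessions; four months (about 120 days); a 24-hour look-back at each pre-survey; workshop length of 2 hours.

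**Assumptions:** home session length is not stated, so 2 hours is borrowed from the workshop. The gaps between starts below are illustrative.

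**1. Can four sessions fit in one day?** 4 × 2 h = 8 h. Yes.

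**2. Distinct hours covered.** For four starts g hours apart, the 24-hour windows together cover 24 + 3 × min(g, 24) hours, out of 4 × 24 = 96.

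| Gap between starts | Distinct hours of 96 |
|---|---|
| 1 h | 24 + 3 = 27 |
| 2 h | 24 + 6 = 30 |
| 4 h | 24 + 12 = 36 |
| 6 h | 24 + 18 = 42 |
| 24 h | 24 + 72 = 96 |

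These gaps run from start to start. If sessions last 2 hours with a 2-hour rest between them, starts are 4 hours apart and the 36-hour row applies.

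**3. Overlap at 2-hour starts.** Adjacent windows share 22/24 = 92% of their hours; the first and fourth share 18/24 = 75%. An episode within the 18 hours before the first start lies in all four windows and gives four yes answers. With starts at least 24 hours apart, it falls in one window only.

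**4. Adding the workshop pre-survey.** If it was at least 24 hours before the first home start, five surveys cover 24 + 30 = 54 distinct hours of 5 × 24 = 120.

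**5. Hypotheses 2 to 4, as a range only.** Suppose every session ends at the same level and a share c of the first session's change persists at each later start. The mean change over four sessions, relative to the first, is (1 + 3(1 − c))/4.

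| c | Mean change relative to first session |
|---|---|
| 0% | 100% |
| 25% | 81% |
| 50% | 63% |
| 75% | 44% |
| 100% | 25% |

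The documents do not give c. If each session instead produced the same change from wherever it started, there would be no shrinkage.

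**6. After a minimum gap.** At 24 hours all 96 hours are distinct, and the first and last starts are at least 3 days apart. At 7 days the four sessions need 3 × 7 + 1 = 22 of about 120 days.

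**The case against.** The strongest reply is that free timing is deliberate. This is an exploratory pilot that sets out to observe real-world use, and when patients choose to use the kits is part of the observation. Acceptability is judged partly by survey completion, so a payment rule touches something being measured. The plan also expects high attrition and schedules contacts about barriers, which points to too few sessions more than to bunching. This stands as a reason not to restrict artmaking and to keep the rule light. It does not resolve the overlap, because a limit on paid pairs leaves patients free to make art at any time.

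The objection also succeeds against four stronger readings that a reader might infer:

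- **That pain, mood and connectedness results are biased by a known amount.** The documents give no effect size or duration of effect. Any shrinkage would be towards a smaller effect, not a false benefit.
- **That close pairs should be dropped from Hypotheses 2 to 4.** Those hypotheses concern change during artmaking, measured immediately before and after. That contrast is valid at any spacing.
- **That the study period for opioid use can collapse to a single day.** The workshop pre-survey carries the same questions, so this would need the home sessions to fall on or next to the workshop day. The item's other purpose, use in connection with artmaking, does not need spaced sessions.
- **That overlap of the last-week BPI questions damages the pain outcome.** Those questions are not pre/post outcomes.

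**Conclusion.** The point holds for Hypothesis 5. The plan allows and pays for four pairs in one day, and 24-hour reports taken less than 24 hours apart repeat the same hours. At 2-hour starts they cover 30 of 96 hours, and one episode can give up to four yes answers. This follows from the look-back window and the absence of a gap; it needs no assumption about carry-over. It does depend on patients actually bunching sessions, and the documents do not indicate how many would.

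For Hypotheses 2 to 4, shrinkage of the mean change is possible but of unknown size, and it justifies a sensitivity analysis only.

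A 24-hour rule removes double counting but does not secure coverage of the four months: four consecutive days would still satisfy it. The span covered therefore has to be reported.

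**What to change.** 1. **Payment rule.** In Section 3 (Overview, In-Person Workshop, At-Home Artmaking), Section 6 (Remuneration) and on the kit reminder, state that the $20 is paid for at most one survey pair in any 24 hours, up to four pairs, and that patients may make art as often as they like.
2. **Timing data.** Record date and start time on every paper and online survey. The documents do not say whether this is done, and the rules below cannot be applied without it.
3. **Hypothesis 5.** In Data Analysis, count only pre-surveys at least 24 hours after the previous counted one, starting from the workshop pre-survey, and report the time span that each patient's counted surveys cover.
4. **Hypotheses 2 to 4.** Keep all pairs. As a sensitivity analysis, show the result without pairs started within 24 hours of an earlier pair.
5. **Optional.** If the sponsor wants Hypothesis 5 to cover more of the study period, use a longer payment gap; 7 days, for example, needs 22 of about 120 days.

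The cost is a sentence in each of these places, a date and time field on the forms, and two lines in Data Analysis. Patients who would have done several sessions in one day will supply fewer paid pairs.

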7. RISK/BENEFIT TO PARTICIPANTS

The study protocol asks that patients reflect on their levels of pain, depression, anxiety, and social connection and as such could bring these experiences to the forefront of patients' minds during study activities and result in discomfort. There is also a small risk of loss of confidentiality, as patients will be recruited in a community setting – the [name] methadone clinic. To address confidentiality, we will remove any names used in the meaning making session during the transcription process and will enclose all written information about the study that is included in the art kits so that they are not immediately viewable by third parties. Audio recording of the meaning making session will be stored in a password protected folder on a password protected computer and destroyed once it has been transcribed. Patients will further be informed that they can refuse to answer any question if it makes them uncomfortable, and will be reminded that their participation is wholly voluntary.

Patients participating in groups and home practice may benefit from potential improvements in pain, OUD, and mental health symptoms. They will derive no specific benefits from completing questionnaires and participating in qualitative interviews.

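### Pre- and post-surveys differ in content at every session: last-week pain items accompany the pain outcome before artmaking but not after, and the uncontrolled paired test cannot separate any resulting shift from artmaking

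*Combined protocol and SAP*

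**What the plan says.** The Data Collection table (Section 3) lists what is collected at the workshop and at each of up to four home sessions. For pain, the workshop entry reads "Questions 1-3 of the BPI Reduced Minus Peg Questions (pre) and question 3 of the BPI Reduced Minus Peg Questions (post"), and the home entry is the same. For opioids, both entries read "Questions asking about current and recent unprescribed opioid use (pre) and level of highness in the moment (pre, post").

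Section 1, Aim 2, shows that the pain asymmetry is deliberate: "questions one and two will be only asked in the pre-survey as these questions ask about pain over the last week", and so their answers are not expected to change across one session.

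The mood items, for example "Single question asking about current level of depression", have no pre/post tag. Hypothesis 3 needs them on both forms.

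Aim 2 places the "6-item Pain Catastrophizing Questionnaire (attached) during the in-person workshop". Section 3 describes the workshops' role in these terms: "they will gather patient characteristic data (demographics, Pain Catastrophizing Survey", along with art experience and openness to mindfulness. Neither place says whether it is completed before or after the pre-survey's outcome items.

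Under Data Analysis (Section 3), pre/post change is tested with paired t-tests, with linear regressions on baseline variables such as demographics. No comparator is named.

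**The concern.** A paired pre/post comparison assumes that the two ratings are obtained in the same way. Here the pre form carries extra content that the post form lacks, and some of it concerns the construct being rated. Recalling a week of pain just before rating pain can change that rating. If it does so on one form only, the mean difference contains a component that comes from the questionnaire.

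The asymmetry is built into every session and applies to every patient. More pairs would therefore narrow the interval around the shifted value without removing the shift. Regression on baseline variables cannot remove it either, because no patient goes without it. Success on Hypotheses 2 to 4 is defined as a significant pre/post change, so a shift of either sign could alter the conclusion.

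**Working it through.** **Step 1. Compare the forms** (Section 3, Data Collection table; Section 1, Aim 2).

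| Item | Pre | Post |
|---|---|---|
| BPI questions 1-2 (last week) | yes | no |
| BPI question 3 | yes | yes |
| Depression, anxiety, IOS-CC | untagged; the hypotheses need both | untagged; the hypotheses need both |
| Unprescribed opioid-use questions | yes | no |
| Highness | yes | yes |
| Pain Catastrophizing Questionnaire (workshop only) | not stated | not stated |

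Two blocks are certainly one-sided: BPI questions 1-2 and the opioid-use questions.

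**Step 2. What can precede an outcome item?** Order within a form is not given; the table is a list of measures.
- BPI numbering puts questions 1-2 before question 3. This is the firmest part of the point.
- If the table's order were the form's order, the opioid-use questions would follow depression, anxiety and IOS-CC, and so could not affect those ratings on the same form.
- On that same reading, and only if it is given with the workshop pre-survey, the Pain Catastrophizing Questionnaire would come just before depression and anxiety.

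**Step 3. Scale.** The plan states no alpha, SD, effect size or justification for about 40 patients, so there is no figure to reproduce. The following is an illustration. Assumed: n = 40 pairs, two-sided 5%, a 0-10 item, SD of change 1.5 to 2.5, no true effect, and a context shift of 0.1 to 0.5 points that raises the pre rating only.

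Standard error = SD/√40: 0.237, 0.316 and 0.395 for SD 1.5, 2.0 and 2.5. The critical t on 39 df is 2.023, so the smallest significant mean fall is 2.023 × SE = 0.48, 0.64 and 0.80 points.

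P(significant fall) = P(T > 2.023), where T is noncentral t on 39 df with noncentrality shift/SE. For example, 0.5/0.237 = 2.11 gives 54%.

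| Shift (points) | SD 1.5 | SD 2.0 | SD 2.5 |
|---|---|---|---|
| 0 | 2.5% | 2.5% | 2.5% |
| 0.1 | 6.1% | 4.9% | 4.3% |
| 0.25 | 18% | 12% | 9% |
| 0.5 | 54% | 34% | 23% |

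A shift in the other direction would hide a real fall instead of creating a false one.

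**The case against.** The strongest reply is that little of the supposed priming is in the documents.

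- **Opioid-use questions.** A reader might infer that these prime the pain and mood ratings. The documents do not support that: order is unstated, and the only order on show puts them after the mood items. Opioid content is also not absent afterwards, since the highness item is on both forms.
- **Pain catastrophizing.** A reader might infer that the post-survey leaves it out. It has no tag, and it could be a separate form or come after the outcome items. Pre-only use is a fair guess from its role as patient characteristic data, but still a guess.
- **Section 7.** The warning that the study "could bring these experiences to the forefront of" patients' minds might be read as the sponsor conceding one-sided bias. It refers to reflecting on levels of pain, depression, anxiety and social connection, which are the outcome constructs asked both times. It does not mention the pre-only items.
- **Direction.** A reader might infer that the bias favours artmaking. Recalling a bad week could raise the current rating or, by contrast, lower it. Patients also meet BPI questions 1-3 and the recent-use question at eligibility screening (Section 4) and then at up to five sessions, so any effect may fade.
- **Priority.** This is an exploratory pilot, the pre-only rule has a stated reason, and the lack of a comparator is the larger threat.

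All of this stands as a limit on the claim. It does not remove the core. The reason given for leaving questions 1-2 off the post form concerns their own answers; it does not address their effect on question 3. And while adding a comparator would be a major change for this pilot, item order is a simple choice.

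**Conclusion.** The point holds as an avoidable asymmetry, not as a demonstrated bias. It is documented that BPI questions 1-2 and the opioid-use questions are pre-only at all sessions, and that the planned paired analysis has no means of separating a question-context effect from artmaking. That questions 1-2 come before question 3 rests on the BPI numbering. Any effect on the mood items through pain catastrophizing depends on two unstated facts: its timing and its position.

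Direction and size are unknown. The 4% to 54% range follows entirely from the assumed shift, SD, scale and alpha, and at the small end (0.1 points) it is only modestly above 2.5%. It shows that a shift of a few tenths of a point could matter with about 40 pairs; it does not show that such a shift occurs. This is a cheap improvement to make before the forms are printed and programmed.

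**What to change.** On every pre and post form, paper and online, in English and Spanish, ask the current-state items first and in the same order: BPI question 3, depression, anxiety, IOS-CC, highness. On the pre form only, follow them with BPI questions 1-2, the opioid-use questions and, at the workshop, the Pain Catastrophizing Questionnaire and the background items. Catastrophizing and background items could instead be collected before workshop day. State the item order and the timing of the Pain Catastrophizing Questionnaire in Section 3.

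The cost is reordering the questionnaires before printing and programming. The small downside is that BPI question 3 is asked out of its numbered sequence.

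The change makes the pre and post ratings comparable in what precedes them on the form. It does not deal with regression to the mean, expectancy or the passage of time. Pre-only items would still be answered before the artmaking, so a lasting effect on the post rating is not excluded. Results should be reported as uncontrolled pre/post change.
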